These adverse events do not occur randomly across the day (28) but are clustered around a morning vulnerable period (29-31). This daily pattern of vulnerability likely emerges from three sources. First, CV responses to rapid changes in behavior during the morning—including waking from sleep, posture changes, and sudden physical activity—precipitate adverse events (17,18,32-34). Second, the time of day itself represents a time of vulnerability to CV events due to the function of the circadian clock that times 24 h rhythms in physiology and behavior (Clock-Risk Model) (35,36). The likeliest scenario, is a mixture of these, in which a behavior like exercise is harmless at most times of day, but may trigger an adverse event in this clock-defined window of vulnerability (Clock-Reactivity Model). Thus, we aim to determine how obesity affects: (1) circadian rhythms of CV function and (2) the time-of-day dependent reactivity of the CV system to typical physical stressors i.e., posture and exercise.

Studying circadian rhythms in humans. To separate the endogenous circadian and behavioral influences on CV function in humans, our research team has applied ‘Forced Desynchrony’ protocols – as proposed in the current study. This separation is achieved by scheduling all behaviors evenly across all phases of the circadian cycle via numerous recurring days that have non-24 h periods while the participant remains in dim light to avoid circadian entrainment to light (37,38). Using this technique, we discovered in healthy lean individuals that certain CV risk factors surge around the vulnerable morning period for increased MI and CV deaths, including circulating cortisol (39), sympathetic activation, cardiac vagal withdrawal, heart rate (HR) (39), (40), platelet aggregability (41) and the pro-thrombotic plasminogen activator inhibitor-1 (PAI-1) (42). These circadian rhythms are presumably beneficial in healthy people as they prepare individuals for rapid physiological responses associated

[figure not shown]

Fig. 1. The FD consists of a baseline night and day, then ten 5 h 20 m cycles of sleep (black) and wake (gray). Stressors are scheduled each wake period. Lights are dim (≤ 3 lux). Letters indicate PET scanning for cardiac sympathetic function. Each participant undergoes up to 3 scans across the entire FD, 16 h apart across the circadian cycle, in a randomized order (a1, a2 & a3, or b1, b2 & b3, or c1, c2 & c3, balanced among participants).

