Acclimatization and baseline day: Participants report to the laboratory at Oregon Clinical & Translational Research Institute (OCTRI) on day 1 and are admitted to an individual room free of external time cues (e.g., clocks, radios, computers, visitors and sunlight). Participants maintain contact with study investigators. Room temperature is maintained at 21-22.2 °C and light intensity set at ≤ 3 lux during scheduled wakefulness and <0.2 lux (darkness) during scheduled sleep opportunities. Participants will be instrumented for full polysomnography, and a Holter monitor throughout the study. Our laboratory suites have a porthole for 24 h blood sampling without disturbing sleep and an IV line will be inserted and kept patent by a heparin solution.

Investigators/nurses are present in the lab or in a central control room 24h/day to monitor subject health, data acquisition, provide meals, collect biologic specimens, perform tests, and record sleep. A physician is always on call when a participant is in the laboratory. An extensive series of written protocols and checklists and team practices are used to ensure uniformity in execution of standard procedures.

FD Protocol (Fig. 1): Designed by Kleitman (37), the FD protocol desynchronizes the sleep-wake cycles from the circadian pacemaker and is performed in dim light to ensure the circadian pacemaker 'free-runs' at its intrinsic rate of ~ 24.1 h (43). At ~ 6 PM on day 2 after having been awake for 10 h, a participant's sleep-wake cycle is scheduled to a period of 5 h 20 min with a 2:1 ratio of wake: sleep-opportunity.

Imaging: PET imaging of the heart (detailed below in section 6h) will occur up to 3 times for each subject across the FD protocol (Fig. 1). The scans will be a minimum of 16 h apart (Fig. 1) and represent up to 3 different circadian phases.

Cardiac ultrasound: Myocardial perfusion imaging (detailed in section 6i) may occur up to 3 times for each

participant across the FD protocol.

5. Study Population

a. Number of Subjects

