p. **Discharge:** Following the last FD waking period, participants will be given 9 hours of recovery sleep during their extended habitual sleep time. The additional hour beyond habitual sleep time will account for possible sleep deprivation during the protocol and account for the natural drift the participant may experience as a result of a free running circadian system (a result of constant dark or dim light). Upon awakening participants will have the opportunity to shower and eat a breakfast of their choosing. Following the meal, participants will complete the *Stanford Sleepiness Scale* and have a final nursing assessment. If an individual does not rate a score of 1 or 2 (Feeling active, wide awake OR Functioning at high levels), participants will be given the opportunity for additional rest, provided a cab ride home, or picked up by a family member/friend. We may also use a 10-minute psychomotor vigilance test (PTV) initially provided during the second screening visit. Failure to obtain within 10% of their initial score would be similar to having a blood alcohol score above the legal limit. If the participant insists on leaving and driving themselves home, they must sign a waiver stating that upon research and nursing staff, and physician advice they chose to drive home and assume liability. Finally, upon departure participants will be provided a card that once more (originally in consent form) provides staff contact information. The card will also remind participants of possible residual side effects associated with the study.

7. Data and Specimens

a. Handling of Data and Specimens

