- iii. **Specimen Handling:** Blood and urine samples will be identified only by the code assigned at the initial phone screen. Processing and handling of samples will be done by the OCTRI nursing and core lab staff. Samples will be stored and maintained by the OCTRI core lab -80 degree freezers. Access to study samples at OHSU will be limited to OCTRI core lab staff and study personnel listed on the IRB approved protocol. Coded biological samples may be sent to outside labs for analysis.

b. **Sharing of Results with Subjects**

With their consent, we will make known to the participant some of the information we have gathered from the physiological testing during screening and in the laboratory. There is a chance that the pre-study screening or the various blood and urine samples taken during the study will reveal some medical abnormality. This information will be conveyed to the participant, together with a recommendation to discuss the results with a physician if appropriate. Specifically, since genetic information obtained does not have medical or treatment importance at this time it will not be shared with the participant.

8. Data Analysis

Analysis of circadian rhythmicity: Forced desynchrony data is composed of circadian effects (intrinsic period ~24 h), evoked effects (5 h 20 min behavioral cycles) and 'noise'. The intrinsic period of the circadian pacemaker will be assessed with standard techniques as used for 20 years by the Principal Investigator (65,66). This intrinsic period, derived from melatonin, will be used to assign a circadian phase (from 0° to 360°) to each minute of the study, with 0° corresponding to the minimum of the waveform fitted to the DLMO data from the FD portion of the study. Analysis then proceeds in two ways. (A) Binning: Data for each variable and each participant will be 'binned' according to circadian phase and an average value per bin will be calculated. Data will then be averaged across participants. Bin size will be determined by the nature of the data being analyzed; in most cases we have found that a bin size of 60° (~4 h) allows sufficient detail while at the same time provides data for each participant in each bin. (B) Cosinor analysis to estimate rhythm amplitude and phase (67): Using regression techniques, time series data, not necessarily evenly spaced, can be fit to the function. This can be done within-subject, so standard deviations of amplitude and phase can be estimated (68).

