12. The amount of blood drawn should not significantly alter blood volume, although there may be a small decrease in the hematocrit. We will only recruit participants with normal levels of hemoglobin, hematocrit, and ferritin. The participants' hemoglobin and red blood cell concentration will be carefully monitored throughout the study as needed, and blood drawing, with the exception of the blood drawn

during the 3 PET scanning procedures (1mL each scan, total of 3mL), will be discontinued if at any time the hemoglobin and/or red blood cell concentration should fall below established guidelines in addition to falling more than 1.3 gm/dL below their hemoglobin levels at admission. In this case, upon discharge, participants will be given information on their hemoglobin levels and will be encouraged to see their primary care provider. In addition, participants are encouraged to eat iron rich food before and after the study.

- ii. **Polysomnography:** The tape and special paste used to attach the EEG electrodes may cause some minor discomfort, skin irritation, and the glue used to hold electrodes to the scalp may leave a flaky residue for several days. The adhesive ECG pads may cause some skin irritation; the participant will be instructed to ask for a change in their placement if this occurs. To prep skin for ECG electrodes, participant skin may need to be shaved which may cause some minor discomfort and skin irritation.
- iii. **Flow mediated dilation (FMD):** The blood pressure cuff on the forearm is inflated to suprasystolic pressure. This may cause numbness below the site of inflation, and slight pain at the cuff site. In our experience, this discomfort does not last for more than 5 minutes after deflation of the cuff. Standard guidelines will be followed to measure FMD in a safe manner. The gel used for the ultrasound imaging may cause some skin irritation and redness. In case participants are allergic to one particular gel, a different gel will be used. The gel will be wiped off after the measurement.
- iv. **In-lab Protocol**
 - 1. The participant may undergo some weight loss over the course of the study. This is typically due to a loss of fluid as a result of differences in the sodium content between the laboratory diet and the participants' regular diet. However, it is also possible that participants may experience a modest loss in actual body mass.
 - 2. The participant's mood, appetite and weight will be monitored.

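### The analysis text states no time-in-protocol term for the forced desynchrony, so roughly a tenth to a sixth of any steady drift in level would be read as 24 h amplitude

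*Combined protocol and SAP*

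**What the plan says.** Section 8 (Data Analysis, analysis of circadian rhythmicity) opens with a three-part description of the FD data: a circadian part with a period near 24 h, "evoked effects (5 h 20 min behavioral cycles) and 'noise". Two analyses follow. In (A), data are averaged by circadian phase, where "a bin size of 60° (~4 h) allows sufficient detail", and then across participants. In (B), a cosinor regression is used, for which "time series data, not necessarily evenly spaced, can be fit to the function"; no function is printed after these words in the text available. Neither analysis mentions elapsed time, cycle number, trend or de-trending. The mixed model for β-reserve, later in the same section, names circadian time as its only independent variable.

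The Fig. 1 legend gives a baseline night and day, "then ten 5 h 20 m cycles of sleep (black) and wake (gray"). Section 4 starts this schedule for everyone at one time: "At ~ 6 PM on day 2 after having been awake for 10 h". Order is randomized and balanced for the PET scans only.

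Elsewhere the protocol allows for gradual change during the stay. Section 11a.iv says "The participant may undergo some weight loss over the course of the study", mainly from fluid. Section 11a.i allows for a small fall in hematocrit from blood sampling. Section 6p lengthens recovery sleep to "account for possible sleep deprivation during the protocol". None of these is quantified or linked to the analysis.

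**The concern.** An FD schedule separates the circadian and behavioral cycles from each other. It does not separate either from elapsed time unless the record spans a whole number of circadian cycles or the model contains elapsed time. Here it spans about 2.2 cycles, so a trend is correlated with a 24 h cosine and part of it is absorbed into the fitted rhythm. Because all participants start at about the same clock time, the absorbed part falls at a similar phase in those whose levels drift in the same direction. Averaging over 14 people then does not remove it.

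Two things are at stake. The first is the hypothesis in aim (a) that endogenous rhythms exist in each group. The second is the comparison of rhythm amplitudes between obese and lean participants, which section 9 names as Aim 1.

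**Working it through.** **Inputs from the documents.** Ten cycles of 5 h 20 min; wake:sleep ratio 2:1; start about 18:00; intrinsic period about 24.1 h; n = 14 per group; target differences of 10 mmHg and 10 bpm.

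**Assumptions.** Total drift D over the FD; drift shape (linear, or saturating with time constant 12 or 24 h); each cycle begins with sleep; period varied from 23.7 to 24.5 h.

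**The plan's own figure.** Section 9 gives 80% power at 1.41 SD with 14 per group and level 0.00833. A two-sided two-sample t-test gives power 0.7995 at 1.41 SD, so the figure reproduces. This point does not affect it.

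**Step 1: length.** 10 × 5.333 h = 53.33 h, and 53.33 / 24.1 = 2.21 cycles.

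**Step 2: leakage of a linear drift.** Awakening k falls at t = 1.78 + 5.33(k − 1) h after FD start. Take y = D·t/53.33 with no rhythm and fit y = m + a·cos(2πt/24.1) + b·sin(2πt/24.1) by least squares. At the ten awakenings a = 0.052 D and b = −0.111 D. The amplitude is √(0.052² + 0.111²) D = 0.123 D, or 0.246 D peak to trough. An upward drift peaks near 13.7 h clock time.

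**Step 3: sensitivity.**

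| Sampling and drift | Amplitude | Fitted peak (clock h) |
|---|---|---|
| 10 awakenings, linear | 0.123 D | 13.7 |
| 9 awakenings, linear | 0.156 D | 11.0 |
| Every 30 min, linear | 0.107–0.123 D | 14.4–15.4 |
| All runs (periods 23.7–24.5 h, linear or saturating) | 0.09–0.18 D | 9.7–15.9 |

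The 60° bin means of a pure linear drift differ by about 0.23 D. The fitted 9 AM minus 9 PM contrast, close to one named in section 9, is 0.085 D for linear drift at ten awakenings, with a range of −0.05 to 0.34 D over all runs.

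**Step 4: in outcome units.** For an assumed D = 5 mmHg, amplitude is 0.123 × 5 = 0.6 and peak to trough 0.246 × 5 = 1.2 mmHg. For D = 10 mmHg they are 1.2 and 2.5 mmHg. The same numbers apply in bpm.

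**Step 5: tests that a rhythm exists.** The plan names no test. A Hotelling test on 14 participants' cosine and sine coefficients was simulated at a nominal 5%, with ten awakenings and an assumed between-person phase SD of 1 h. Without a trend term the false-positive rate is about 6% when D is 0.5 residual SD, 9–11% at 1 SD, 18–19% at 1.5 SD and 29–30% at 2 SD. With a phase SD of 2–3 h and D = 1 SD it is 8–9%. With a linear term it returns to about 5%.

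**Step 6: group contrast of amplitudes.** A false component of 0.6 (D = 5) combines with a true amplitude of 5 to give anything from 5 − 0.6 = 4.4 to 5 + 0.6 = 5.6, depending on the true phase. Equal drift therefore cancels between groups in the cosine and sine coefficients, but not exactly in the amplitudes. Unequal drift biases both.

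**Step 7: effect of a linear term.** Fitted jointly, it reduces leakage of linear drift from 0.123 D to zero. The variances of the cosine and sine coefficients rise by 2% and 8% at ten awakenings, and by at most 9% if the sampling point within the cycle moves; √1.09 = 1.04. With nine awakenings the rise is up to 21% (√1.21 = 1.10). For saturating drift the linear term leaves 0.02–0.08 D. A one-off shift confined to the first awakening leaks 0.167 of its size without the term and 0.180 with it.

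**The case against.** The strongest defense is that the three-part sentence describes FD data in general and is not a model specification. The equation is not in the text available, and the section relies on cited methods. That stands: the documents support saying that no trend term is stated, not that the fitted model lacks one. Still, the stated decomposition has no place for a trend, and binning has no equation that could hold one.

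Three stronger readings are tempting, and the documents support none of them.

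- **A reader might infer that drift is fitted wholesale as rhythm.** Only 9 to 18% of it becomes amplitude; the rest goes to the mean and the residual.
- **A reader might infer the same false phase in every participant.** Opposite drift moves the peak by 12 h, circadian phase is assigned individually from melatonin, and the fitted peak shifts with sampling time, period and drift shape.
- **A reader might infer that the obese-lean comparison is already biased.** That needs mainly unequal drift, and nothing in the documents says the groups lose fluid or sleep differently.

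The passages on weight, hematocrit and sleep speak of what may happen, and none concerns BP, HR or flow-mediated dilation. Reactivity measured as change within a test largely removes slow drift in level, and PET is partly protected by its balanced order. The bias is also small beside the 10 mmHg and 10 bpm targets. These points limit the size and scope of the concern; they do not remove it.

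**Conclusion.** The concern holds in limited form. The plan does not state how change over the FD is handled. With 53.3 h from a common start, about 12% of a linear drift over that time, and 9 to 18% across the monotone shapes and sampling schemes tried, would appear as 24 h amplitude. The main exposure is the within-group claim that a rhythm exists, and its estimated phase. The amplitude contrast between groups is exposed chiefly if drift differs by group.

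All sizes are multiples of an assumed D. At 5 to 10 mmHg the false amplitude is 0.6 to 1.2 mmHg, which will not by itself produce a 10 mmHg difference. The false-positive rates also rest on the assumed residual SD ratio, phase spread and test. The change is worth making because it is cheap and can be specified without any knowledge of the drift.

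**What to change.** 1. Print the full cosinor or mixed model. Include hours since FD start (linear, with a group interaction) as fixed effects, fitted jointly with the circadian and evoked terms.
2. For binning, subtract the trend estimated from that joint model. Do not de-trend each participant separately beforehand: trend and cosine are correlated, so that step would shrink a true rhythm by about 1–8%.
3. Add a sensitivity analysis with a nonlinear trend, or one that excludes the first cycle, because a linear term does not remove a first-cycle effect and only partly removes saturating drift.
4. State whether the same adjustment applies to the β-reserve model. With up to three scans per participant, the trend would have to be pooled across participants.

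The cost is one term with its interaction, a few lines of SAP text, and standard errors of the cosine and sine coefficients up to about 4% wider with ten awakenings (about 10% if only nine are usable). No change to procedures or sample size is needed.

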with anticipated rigorous daytime behaviors. But these same rhythms might be deleterious in obese individuals due to their increased CV risk. Despite the information on CV rhythms in healthy and generally lean subjects, how obesity alters the timing or amplitude of these rhythms is unknown.

4. Study Design

The goals of this study are to elucidate circadian rhythms in CV risk markers in obesity. To meet this goal, we will evaluate endogenous circadian rhythms, responses to behaviors and the interaction of behaviors and endogenous circadian rhythms in hemodynamic variables (BP, HR, vascular endothelial function) and primary physiological regulators, in obese and lean individuals. To study independent effects of the circadian clock, we will conduct a 5-day forced desynchrony protocol (FD, **Fig 1**) where all behaviors such as arousal from sleep, eating a meal, performing an exercise test, and sleep will occur evenly spaced across the entire circadian cycle by scheduling 10 recurring 'day' of 5 h 20 min. Repeated measurements of CV variables throughout the 10 wake/sleep cycles allow for assessment of independent effects of circadian rhythms and scheduled behaviors. Due to repeated measures, we propose to measure selected clinically relevant CV variables that are reliable, relatively noninvasive, and independent.

Baseline routine: To stabilize circadian rhythms, participants will maintain a consistent sleep-wake schedule for at least 1 week prior to admission to the laboratory. The bedtime will be determined by a participant's habitual bedtime with 8-h time in bed. To ensure compliance to this schedule, each participant's activity will be monitored by wrist Actigraphy (ActiGraph wGT3X-BT, ActiGraph, Pensacola, FL). Actigraphy will provide an estimate of daily activity levels and sleep characteristics in real world settings. Participants fill out a sleep diary every day, and call into a time-stamped voice-mailbox when going to bed and getting out of bed. If more than one deviation (>1 h) from the target times are detected per week, the subject is asked to repeat the screening schedule. To identify daily BP patterns, subjects will wear an ambulatory BP monitor (Spacelabs Healthcare, WA) for 48-h during this home routine.

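### For variables recorded in both sleep and wake, averaging in 60° circadian bins leaves unequal shares of sleep in the bins, so part of the sleep-wake effect stays in the binned profile

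*Combined protocol and SAP*

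**What the plan says.** Section 8 (Data Analysis, paragraph on circadian rhythmicity) describes the forced desynchrony data as circadian effects together with "evoked effects (5 h 20 min behavioral cycles) and 'noise". A circadian phase is assigned "to each minute of the study". Under method (A), each participant's data for each variable are binned "according to circadian phase and an average value per bin will be calculated", and the bin values are then averaged over participants. Bin width may vary with the data, but "in most cases we have found that a bin size of 60° (~4 h) allows sufficient detail". Method (A) mentions no split by sleep and wake, no adjustment for time since waking and no check of balance. Method (B) is a cosinor fit; its function does not appear in the available text, so whether it has an evoked term cannot be told.

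The design is meant to supply the balance. Section 4 has behaviours "evenly spaced across the entire circadian cycle by scheduling 10 recurring 'day' of 5 h 20 min". In its FD Protocol paragraph the "sleep-wake cycle is scheduled to a period of 5 h 20 min with a 2:1 ratio of wake: sleep-opportunity", and the circadian pacemaker is expected to run at its "intrinsic rate of ~ 24.1 h". The legend of Fig. 1 gives a baseline night and day, "then ten 5 h 20 m cycles of sleep (black) and wake (gray").

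Section 6 (item l, Sleep) has heart rate, blood pressure and autonomic measures recorded in sleep as well as wake, with blood sampling continuing about every 2 h. Endothelial function is not measured in sleep.

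**The concern.** Forced desynchrony is used so that behaviour averages out of the circadian estimate. In a simple bin mean this happens only if every bin holds the same mix of sleep and wake. If the mix differs, part of the sleep-wake difference appears as a circadian difference.

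The comparison most exposed is one that Section 9 names among the main outcomes: the vulnerable phase near 9 AM against other phases, for example 12 h later. With 60° bins those two phases lie three bins apart. Systolic blood pressure and heart rate are main outcomes and are recorded in both states.

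**Working it through.** **Inputs from the documents.** Cycle length T = 5 h 20 min, of which one third (1 h 46 min 40 s) is sleep opportunity; ten cycles; circadian period about 24.1 h; bin width 60°.

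**Assumptions (not in the documents).** The position of phase 0° relative to the schedule (all positions tried); the size of the sleep-wake difference (10 units, mmHg or bpm, for scale); the spread of phase between participants (SD 1 to 2 h); periods other than 24.1 h (23.8 to 24.5 h).

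**The plan's own figures.** 60/360 × 24.1 h = 4.02 h, which agrees with about 4 h. Over ten cycles each 60° bin receives 1 to 3 awakenings, so the statement that every participant has data in every bin also holds.

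**Why 60° does not balance, by hand.** Take a period of 24.0 h and nine cycles.
- 9 × 5 h 20 min = 48 h, exactly two circadian days. Each cycle advances phase by 5.333/24 × 360 = 80°, so nine cycles place any given cycle time on a 40° grid.
- 24/5.333 = 4.5, so each phase is visited twice, half a cycle (2 h 40 min, or 40°) apart.
- Adding the two visits gives a pattern that repeats every 160 min. For 106.67 min one of the two visits is asleep; for 53.33 min neither is.
- A 60° bin spans 240 min, which is one whole pattern (160 min) plus half of one (80 min). The half contributes between 80 − 53.33 = 26.67 and 80 min of sleep.
- Each bin holds 2 × 240 = 480 min, so its sleep share lies between (106.67 + 26.67)/480 = 27.8% and (106.67 + 80)/480 = 38.9%.
- The pattern alternates from bin to bin. Opposite bins are three apart and so always of different type; their gap runs from 0 to 38.9 − 27.8 = 11.1 points, depending on where 0° falls.
- Bins of 40° hold exactly one pattern, hence 33.3% sleep in each.

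**The schedule as planned.** Ten cycles last 53.33 h. The tenth covers about 80° of the circle once more than the rest. Laying the schedule on a fine time grid at 24.1 h and trying all positions of 0°:
- Sleep share per 60° bin: 19% to 50%.
- Largest opposite-bin gap within a participant: 4 to 22 points, mean 12.
- Example with 0° displaced by 40°: 48.7, 20.9, 40.1, 27.8, 37.7 and 27.8%. The opposite-bin differences are 48.7 − 27.8 = 20.9, 20.9 − 37.7 = −16.8 and 40.1 − 27.8 = 12.3 points.
- Periods of 23.8 to 24.5 h give largest gaps of 2 to 22 points. Starting with sleep or with wake makes no material difference.

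**Group mean of 14.** The largest opposite-bin gap averages about 7 points at a phase SD of 1 h and a little under 6 at 2 h.

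**Conversion to outcome units.** Artefact = gap × sleep-wake difference. At an assumed 10 units:
- Group mean: 0.06 to 0.07 × 10 = 0.6 to 0.7 units.
- Worst-aligned single participant: 0.22 × 10 = 2.2 units.

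These scale in proportion to the sleep-wake difference.

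**Other bin widths.** Nine consecutive cycles with 40° bins at 24.1 h keep the sleep share at about 31.6 to 35.4%. With all ten cycles, 40° bins still range from about 22% to 50%.

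**The case against.** The best reply is that sleep and wake values may never be pooled. Section 6 describes many measures by state: heart rate and blood pressure in sleep are collected to compare with wake in the same posture, heart rate variability is analysed by condition, and baseline values come from a fixed supine period after each awakening. Binning within state is a plausible intention, and bin width is left flexible. But Section 8 is where the analysis is specified. It gives phase to all minutes and sets no restriction by state, so pooling is what method (A) says as written.

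A reader might infer that the main outcomes as a whole are compromised. The documents do not support that. Flow-mediated dilation and values on awakening are taken at one fixed point in each cycle and are unaffected if binned alone. Amplitude and phase are estimated in (B), not (A). Over exactly nine cycles the alternation is an 8 h pattern, orthogonal to a 24 h cosine; the tenth cycle breaks that exactness.

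A reader might also carry the 2-unit figure over to the group results. It describes one worst-aligned participant; differences in phase between people shrink the gap without removing it. Nor are the 10 mmHg and 10 bpm in Section 9 expected sleep-wake differences. They are differences to be detected, so the 10 units used for scale here are an assumption.

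Finally, both groups follow the same schedule, so part of the artefact cancels in obese-lean contrasts. That stands if phase and sleep-wake response are alike in the two groups. The study asks whether obesity changes rhythms and responses, so this should not be taken for granted.

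**Conclusion.** The point holds for variables recorded in both sleep and wake: heart rate, blood pressure, heart rate variability and the roughly 2-hourly blood markers. For these, method (A) as written yields a profile that still contains part of the evoked effect, and contrasts between opposite phases are the most exposed.

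The likely size is modest. The group-level artefact is well under a tenth of the 10-unit target in Section 9 if the sleep-wake difference is 10 units and phase SD is 1 to 2 h. It would be larger with a larger sleep-wake difference or more uniform phase. The imbalance itself follows from the documented schedule and bin width; its exact value depends on where 0° falls. It should be corrected before analysis, but it is not evidence that the design fails or that the obese-lean comparisons are invalid.

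**What to change.** In method (A), state that the evoked component is removed before phases are compared, in one of two ways:
- bin within behavioural state, or within time since scheduled waking; or
- fit circadian bin and time within the 5 h 20 min cycle in one model and report adjusted bin means. Both sets of terms are estimable on the planned schedule. This removes the average evoked effect; where that effect may itself vary with phase, use the first option.

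In method (B), write out the cosinor function and make sure it carries the same evoked term.

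For continuously recorded variables, 40° bins over nine consecutive cycles are an alternative, at the price of discarding a cycle. Moving to 40° while keeping all ten cycles does not solve the problem.

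Averaging sleep and wake separately and recombining them 2:1 is weaker. It equalises the sleep share, but the first half of wake still makes up 32% to 68% of wake minutes across bins, so effects of meals, exercise and posture can remain. With sampling every 2 h or so, some bins may contain no sleep sample.

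The cost is a few lines of analysis text and code, with no change to data collection. Bin values become slightly noisier, mainly for the sparsely sampled blood markers.
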